Data collection. Prior to beginning any research procedures, students will provide their informed consent online via Qualtrics. Participants will be required to login to Qualtrics via HarvardKey Shibboleth, which will be configured to only allow currently active Harvard accounts. Once consent has been obtained for an individual student, they will be directed to an online survey for the study **baseline assessment**. The baseline survey will be open for two weeks. Students assigned to the intervention group will receive an access code in the email, allowing them to access the online platform and set-up their account. The intervention group will then be active for seven weeks, after which the **posttest survey** will open to the intervention group and waitlist group for one-two weeks. There will then be a pause in study activity and data collection from mid-November through winter break. Thereafter, there will be a **2-month follow-up survey** and students who were assigned to the waitlist group will gain access to the online intervention for seven weeks. After this delayed access group completes the intervention, there will be a **5-month follow-up survey** for all participants from both conditions. After the fourth survey, subsets of participants may be invited to additional compensated opportunities to provide further feedback as research data. See timeline table below.

Activity	Timeline
Promotion	August 16 – Sept 6
Recruitment + Baseline Survey	Sept 7 – Sept 17
First Intervention Round	Sept 20 – Nov 7
•Weekly goal-setting & Time management	Sept 20 - 26
•Unhelpful thinking habits	Sept 27 - Oct 3
•Quality time on values & fun	Oct 4 - Oct 10
•Relaxation strategies & Mindfulness	Oct 11 - Oct 17
•Sleep hygiene	Oct 18 - Oct 24
•Physical exercise	Oct 25 - Oct 31

•Wrap-up	Nov 1 - Nov 7
Posttest Survey	Nov 8 – Nov 19
Break	
2-month Follow-up Survey	Jan 24 - Feb 4
Second Intervention Round	Feb 7 – Apr 3
•Weekly goal-setting & Time management	Feb 7 - Feb 13
•Unhelpful thinking habits	Feb 14 - Feb 20
•Quality time on values & fun	Feb 21 - Feb 27
•Relaxation strategies & Mindfulness	Feb 28 - Mar 6
•Sleep hygiene	Mar 7 - Mar 13
Spring break	Mar 14 – Mar 20
•Physical exercise	Mar 21 - Mar 27
•Wrap-up	Mar 28 - Apr 3
5-month Follow-up Survey	Apr 4 - 15
Additional feedback from subgroups TBD	April - May 2022

Conditions

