Every Monday participants receive an email directing them to the instructions section of the online platform. Each module presents a checklist of activities for participants to complete as well as tips and suggestions for how to practice each module's skill. At the beginning of the week, participants make a "plan" indicating which activities/skills they intended to try and any barriers they expected to encounter. Throughout the week, participants can visit their user dashboard to log skills practice for the current module (within a seven-day grace period) along with ratings of their mood and stress levels, which are plotted in their self-monitoring graph. NOTE: Students do not complete any of the activities within the app (e.g., users do not record their unhelpful thinking habits during week 3), but rather they submit a log after practicing a skill outside of the app. At the end of each module participants are prompted to complete weekly check-in questions about their personal goal progress. Weekly prize drawings (items of \$10-40 value) will be offered to all participants submitting a weekly check-in. Students who had log activity for all modules will be eligible for the completer prize drawing (items of \$100-200 value).

There is also a "Campus" section of their dashboard that provides students with: info about relevant campus resources; a notification center with campus-specific messages and updates; and an anonymous livestream of all campus users' activity, to provide a sense of community. See screenshots of the online platform in the **Supplemental Materials** uploaded.

Finally, residential staff will be encouraged to offer complimentary programming (e.g., relevant themed study breaks), if they are so interested in doing so. These events will not involve any data collection, but the PI will contact residential staff (through approved coordination with the Dean of Students office) to document which houses/dorms held additional events, so that such information can be treated as a covariate in data analyses.

Waitlist group. Participants in this group will receive no intervention or communications between their baseline randomization and the invitation for posttest survey. They will be provided access to the online program after completing the posttest survey.

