6. RISK AND BENEFIT ASSESSMENT

6.1 Describe the foreseeable risks associated with your study. Please include discussion of any physical risks and non-physical risks, such as economic, psychological, social, and legal harms.

Loss of confidentiality is always a risk in studies using human subjects.

Participants may experience **mild discomforts** such as:

- mild boredom or fatigue when completing surveys
- mild annoyance for receiving survey reminder emails
- mild discomfort upon self-reflection about emotional functioning as prompted by surveys

Although we will not be prompting for sensitive data in our surveys, students may of their own volition self-report **potentially sensitive risk data** within open-ended response fields in posttest and follow-up surveys. We do not anticipate such cases being common though, given that the two open-ended questions that we are posing is unlikely to prompt sensitive date. For reference the two questions are: (1) “Overall, what was the most helpful part of this program? What did you like best? What most encouraged you to complete the program?” and (2) “And what was/were the biggest barrier(s) to completing the program? What would need to change to make this program better?”

We do not anticipate any serious risks. Supporting this claim, in a prior open trial and a prior randomized controlled trial there were no students reporting adverse events due to the intervention (as documented by open-ended responses in posttest feedback surveys).

6.2 Describe the steps that you will take to minimize risks to your participants (for example, using pseudonyms or a coding system, etc.)

Loss of confidentiality will be minimized by the following procedures:

1. All consent/assent forms and surveys will be electronic via the Harvard Qualtrics, which is encrypted and will only be accessible by the PI.
2. The Harvard Qualtrics surveys will be configured to use an auto-generated participant ID, kept separate from the ID key (which is associated with their Harvard Key email address)
3. All datasets downloaded on the PI's laptop for analyses (over a secure wifi connection) will have all identifying data (e.g., names, emails) removed.
4. See DAT20-0492 uploaded documentation for platform security info.
5. The master dataset will be password-protected and stored on the PI's Harvard OneDrive.
6. Any qualitative findings will be presented in an aggregated and de-identified way. Selected quotes will be accordingly redacted as necessary.

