Mild discomforts due to survey fatigue will be reduced by optimizing Qualtrics surveys to be easy to answer and minimizing the number of reminder emails sent. Mild discomforts due to self-reflection about psychological symptoms and stressful experiences will be mitigated by provided resource referral info (more info in next item).

Regarding potential sensitive risk data: We will not be asking any questions that prompt students to report on intent to harm themselves or others. Our consent form will warn students (see the “Clinically-Relevant Results” section of consent form) that their individual responses on their StriveWeekly user accounts or in open-ended survey responses will not be monitored during the study, and thus they should not use such text fields to communicate to the research team or Harvard admin about any health concerns. We will also remind students within the posttest and follow-up survey instructions that they are discouraged from entering sensitive data. Nevertheless, we will provide students with referral information to mental health services (e.g., crisis hotlines, counseling center services) in (A) the auto-email sent after a respondent completes a survey, and (b) under the “campus” section of StriveWeekly’s platform.

6.3 Are provisions needed for medical and/or psychological support resources (for example, in the event of research-related distress or incidental findings)?

Yes

No

6.4 If applicable, what steps will you take if a participant becomes distressed during your study or reports intent to harm themselves or others?

We will not be asking any questions that prompt students to report on intent to harm themselves or others. Our consent form will warn students (see the “Clinically-Relevant Results” section) that their

individual responses on their StriveWeekly user accounts or in open-ended survey responses will not be monitored during the study, and thus they should not use such text fields to communicate to the research team or Harvard admin about any health concerns. Nevertheless, we will provide students with referral information to mental health services (e.g., crisis hotlines, counseling center services) in (A) the auto-email sent after a respondent completes a survey, and (b) under the “campus” section of StriveWeekly’s platform.

6.5 Describe any potential direct benefits to participants in the study. If there are no individual benefits, indicate as such.

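### The referral email is triggered by finishing a survey, so a student who stops partway through baseline may get neither referral route that sections 6.2 and 6.4 describe

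*Protocol*

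**What the plan says.** Section 6.1 of the protocol lists among the foreseeable risks "mild discomfort upon self-reflection about emotional functioning as prompted by surveys". Section 6.2 answers that discomfort from self-reflection on symptoms and stressful experiences "will be mitigated by provided resource referral info". Sections 6.2 and 6.4 then give the same two delivery routes for that information:

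- **Email.** It goes out as "the auto-email sent after a respondent completes a survey".
- **Platform.** Referral details appear in the campus area of StriveWeekly. Section 5.1 (Conditions, Intervention group) describes this as a "section of their dashboard that provides students with: info about relevant campus resources".

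On access to the platform, section 5.1 (Data collection) puts consent first, then the baseline survey, and then says: "Students assigned to the intervention group will receive an access code in the email, allowing them to access the online platform". For the waitlist arm, section 5.1 (Conditions, Waitlist group) says: "Participants in this group will receive no intervention or communications between their baseline randomization and the invitation for posttest survey". It adds: "They will be provided access to the online program after completing the posttest survey". The Data collection text places waitlist access later still: alongside or after the 2-month follow-up survey, "students who were assigned to the waitlist group will gain access to the online intervention for seven weeks".

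**The concern.** The mitigation is tied to finishing the questionnaire that may have caused the discomfort. A student who is upset by the questions and closes the survey is the person the referral information is meant for. That student does not meet the trigger for the email and probably has no account through which to see the campus area.

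The situation is foreseeable. Section 11.4 anticipates incomplete survey responses, but only to withhold payment. The measures include the DASS-21 and a life events checklist with COVID-19 items (section 5.2). There are no exclusion criteria set in advance (section 7.2), so students with high symptom levels can enroll, and some participants may be 16 or 17 (section 7.4). Sections 6.2 and 6.4 also say that individual platform responses and open-ended survey answers will not be monitored. Passive referral is therefore the only support those sections describe.

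What is at stake is a modest element of participant protection. Neither the treatment comparison nor any estimate depends on it.

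**Working it through.** The plan gives no figure to reproduce. The check traces each route in 6.2 and 6.4 against the sequence of events in section 5.1.

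**Dates (section 5.1 timeline).** Baseline survey Sept 7 to Sept 17; first intervention round from Sept 20; posttest survey from Nov 8; second intervention round from Feb 7.

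**Case 1: a student consents, starts baseline and stops partway.**

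| Route | Condition for receiving it | Met at that time? |
|---|---|---|
| Email | Survey completed | No |
| Campus area, immediate arm | Account, set up with an emailed access code | Probably not: the code is described after baseline, and the first round starts after baseline closes |
| Campus area, waitlist arm | Account, available after posttest or later | No, unless the student already has an account from the pilot |

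Two points keep the immediate-arm entry at *probably*. The date on which codes are sent is not stated. Pilot participants remain eligible for the trial (section 5.1) and may already have an account. An immediate-arm student with an unfinished baseline might also be sent a code later, because the text does not make the code conditional on completing the survey.

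**Intervals.**

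- Baseline closing to first round: Sept 17 to Sept 20 = 3 days.
- Baseline closing to the opening of posttest, the next planned contact for the waitlist arm: 13 days (Sept 17 to 30) + 31 days (October) + 8 days (Nov 1 to 8) = 52 days.

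The 52 days is the spacing between planned contacts, not a duration of distress. It applies only to a student who stays in the trial with an unfinished baseline. The documents do not say whether such a student is invited to posttest or sent an access code.

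**Case 2: a waitlist student stops partway through posttest, having completed no earlier survey.** The email is again not triggered. Platform access comes after posttest is completed on one reading of section 5.1, and with the second round from Feb 7 on the other. Neither route is available on either reading, apart from the same pilot exception. This case also depends on the student having been invited to posttest.

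**Number affected.** Not estimable. The documents give no rate of partially completed surveys, and none is assumed here.

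**The case against.** The strongest objection is that the gap may be closed by text outside the documents reviewed. Consent precedes baseline, so anyone who abandons baseline has already been through the consent form, and section 10.7 says a copy is emailed to them. Section 6.2 refers to a part of that form on clinically relevant results. The full survey battery is also a separate upload. Either could list services, and their absence here is not evidence that they do not. This stands as a limit: the point concerns only the routes that 6.2 and 6.4 describe. Neither section names the consent form or the survey pages as a way of delivering referrals. The service-use checklist in section 5.2 does mention some services, but as a question about use.

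Second, the protocol does not say that the email goes to completers alone. That is inferred from the stated trigger. The inference is reasonable, since no message to partial responders is described, but it is an inference.

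Third, the risk is mild on the protocol's own account. Baseline takes about 10 minutes (section 5.3), the DASS-21 has no suicidality questions, the open-ended fields come in later surveys, and the two prior trials recorded no adverse events attributed to the intervention (section 6.1). Students may use any other service throughout (section 5.1). Reminder emails and payment only for completed surveys may also bring some students back to finish, and they would then receive the email. The rule against contacting waitlist students does not clearly exclude reminders while baseline is open. All of this stands and keeps the point at the lowest level of importance.

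The posttest case needs several conditions to hold together and is marginal.

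**Conclusion.** The point holds as a minor improvement worth considering. As described in 6.2 and 6.4, the referral mitigation may not reach a student who stops partway through baseline, because one route needs a completed survey and the other needs an account the student probably does not yet have. In the waitlist arm the next planned contact may be as much as 52 days after baseline closes, for a student who remains in the study.

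The conclusion rests on three readings: that the email is sent only on completion, that access codes are not usable during the baseline window, and that the campus area cannot be seen without an account. The first two are inferred from the trigger and the timeline, the third from the campus area's place in the user's dashboard. If the consent form or the surveys already carry the referral text, naming them in 6.2 and 6.4 would largely settle the matter. Confidence is medium. The gain is in participant protection, with no bearing on the trial's results.

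**What to change.** Show the existing referral text in a footer, or on one page, of every Qualtrics survey, baseline included, with identical wording in both arms. A footer is preferable because it avoids placing crisis-service text directly ahead of the symptom items. Keep the completion email and the campus area. Add the in-survey route to sections 6.2 and 6.4, and list the consent form and its emailed copy there too if they already contain the information.

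The cost is a small edit to the survey template and one line in each section. No new data, staff or survey items are needed. Seeing the text could conceivably influence answers or service use. The chance is negligible, and because the wording is the same in both arms, any influence would be balanced between them.

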7. CHARACTERISTICS OF THE STUDY POPULATION

7.1 Indicate the estimated number of participants, by subgroup if applicable. If it is not possible to estimate the number of participants (e.g., open online survey), please indicate that it is not possible and provide an explanation of why it is not possible.

It is not possible to estimate how many participants will enroll, as it will be open to all Harvard undergraduate students who are interested in enrolling. The maximum sample size therefore cannot exceed the size of the undergraduate student body (~6000). By contrast, the randomized controlled trial at UCLA enrolled 1600+ students from an entire student body of 40,000+. This programming was not centrally sponsored by an equivalent to the Dean of Students Office though, so we expect the relative enrollment rate to be higher by percentage of enrolling students relative to total student body. The secondary analyses on a subset of survey data is estimated to include approx. 125 students endorsing identification with the LGBTQ+ community. We expect to conduct follow up interviews with approximately 20 to 30 participants to achieve saturation.

7.2 Describe the criteria for enrollment – Will you be limiting your enrollment to a certain age range, gender, people with certain health conditions, etc.? Please also describe any criteria that will exclude people from enrollment.

We will recruit undergraduate students who are currently enrolled as fulltime students at Harvard as of the time of recruitment. There are no *a priori* exclusion criteria. *Post hoc* exclusion procedures will remove students with invalid data reporting (e.g., straight-lined responses to surveys, high inconsistency in responses to cross-validation item pairs selected based on content similarity). Additionally, inclusion criteria for secondary analyses assessing outcomes among sexual and gender minority subgroups will include endorsement of belonging to the LGBTQ+ community. Students eligible to participate in the follow up interviews will be those who (a) used the StriveWeekly platform at least

once, (b) completed all study surveys, and (c) either identify as LGBTQ+ or want to provide feedback about program inclusivity for this community.

7.3 Are there any potential vulnerable populations or individuals proposed for involvement in the research? (check all that apply)

- Children
- Wards of the State
- Prisoners/Detainees
- Pregnant Women
- Adults not Competent to Consent
- Non-English Speaking
- Employees of Harvard University (as a focus of the study)
- Undergraduate Students of Harvard University (as a focus of the study)
- Staff or students that are part of your lab or for whom you provide oversight
- Other – (see below):

If “Other” please specify:

CHILDREN

Skip this section if not applicable.

